7.3.2 EXCLUSION CRITERIA

A person will be excluded from the study if he/she:

- Is presently participating in any other clinical or research study including eye related clinical or research study;
- Has never worn contact lenses before.
- Has any systemic disease affecting ocular health.
- Has any active* ocular pathology or severe insufficiency of lacrimal secretion (moderate to severe dry eyes) that would affect the wearing of contact lenses.
- Is using any systemic or topical medications that will affect a study outcome variable, and/or ocular health.
- Has any known sensitivity to fluorescein dye or products to be used in the study.
- Has persistent, clinically significant corneal or conjunctival staining using sodium fluorescein dye.
- Has any clinically significant lid or conjunctival abnormalities, active neovascularization or any central corneal scars.
- Is aphakic.
- Has undergone corneal refractive surgery.
- Is pregnant, lactating, or planning a pregnancy at the time of enrolment (by verbal confirmation at the screening visit).

* For the purposes of this study, active ocular disease is defined as infection or inflammation which requires therapeutic treatment. Mild (i.e. not considered clinically relevant) lid abnormalities (blepharitis, meibomian gland dysfunction, papillae), corneal and conjunctival staining and dry eye are not considered active ocular disease. Neovascularization and corneal scars are the result of previous hypoxia, infection or inflammation and are therefore not active.

7.3.3 REPEATED SCREENINGS

In some circumstances a repeated screening may need to be scheduled. Examples include, but are not limited to:

- a) Incomplete information available at time of screening to determine eligibility (e.g. current lens brands worn, history from current eye care practitioner etc.)
- b) Study procedures unable to be completed in time scheduled for visit;
- c) Study products not available at the time of the screening visit;
- d) A transient health condition which may affect the eye(s) (e.g. a common cold, active allergies, fatigue etc.)
- e) The short term use of medications (e.g. antibiotics, antihistamines etc.)

f) Reassessment of baseline ocular conditions (e.g. corneal and/or conjunctival staining, scars etc.)

The maximum total number of screenings permitted will be 3.

7.4 STUDY MATERIALS

7.4.1 CONTACT LENS

Participants will be randomized to receive either the test or control lens as a matched pair at each visit per a predetermined randomization schedule (Appendix 14). The lenses (test and control) will be labelled as Invigor IA (test) and Invigor IB (control).

The Invigor IA (test) lens is an investigational product and will be subject to pre-clinical assessment before being released for the study. This lens is not commercially available in Canada and therefore an ITA (investigational testing authority) from Health Canada has been received.

The Invigor IB (control) i.e. Select 1 Day lens is approved by FDA and Health Canada, and is commercially available in Canada and the USA, however for the purpose of this study, it has been labelled as Invigor IB and is covered under an ITA issued by Health Canada.

Details of the Invigor IA (test) and Invigor IB (control) study lenses used in this study are shown in Table 1. The test lens is the Invigor IA (test) lens and approved by Health Canada for use in the study.

Table 1: Study lenses used in this study

	Invigor IA (test)	Invigor IB (control) (i.e. Select 1 Day)
Manufacturer	CooperVision	CooperVision
HC License No.	-	81009
Material	somofilcon A	somofilcon A
Health Canada license #	-	81009
EWC (%)	56%	56%
Dk/t (-3.00D)	86.0	86.0
BOZR (mm)	8.6	8.6
Diameter (mm)	14.0	14.0
Sphere power (D)	-1.00 to -6.00 (0.25 steps)	-1.00 to -6.00 (0.25 steps)

7.4.2 CONTACT LENS CARE SYSTEM

No contact lens care system is required for this study as lenses are daily disposable lenses to be worn for a single day only with new lenses worn each day.

7.4.3 CONTACT LENS DISPENSING

The lenses will be inserted directly from the blister pack. The use of saline for rinsing prior to insertion is permitted if necessary. Saline will not be dispensed during the study.

Participants will not be encouraged to use rewetting drops; however, those who habitually used rewetting drops will be allowed to continue using their normal drops. Rewetting drop use will be recorded at each visit.

7.4.4 STORAGE OF LENSES AND LENS CARE SOLUTIONS

The study materials must be stored in a secured area. All lenses and any lens care solutions used to store worn lenses should be stored at controlled room temperature (59-86°F). The lens care solution used will be specified in the implementation protocol.

7.4.5 CLINICAL SUPPLY INVENTORY

The CCLR must keep an accurate accounting of the study product during the study. A detailed inventory (including lenses received, dispensed, unused, and returned to the Sponsor) must be completed for study supplies. The study supplies are to be used in accordance with the instructions given to participants who are under the direct supervision of an investigator.

In the event that lenses need to be replaced due to damage/defects before the next scheduled visit, only the damaged/defective lenses will be replaced. A log of lens replacement will be recorded by the site (CCLR).

7.4.6 DISPOSAL OF CONSUMABLES

This study provides consumables (lenses) to participants for use during the study. Participants will be instructed to dispose of worn lenses (both test and control lenses) daily, but retain the foils of all used lens packs and return them at their next study visit. Lenses worn for the scheduled visits will be collected from the participants and they may be either returned to the Sponsor or disposed, as detailed in the implementation protocol. Lenses with product observations (e.g. moderate lens deposits), product defects, or product quality complaints will be collected and returned to CooperVision at the completion of the study. All unworn lenses will be collected from each study participant. Any extra lenses not used in the study will be returned to CooperVision.

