2 STUDY OBJECTIVE

The purpose of this study is to investigate the overall clinical performance of the Invigor IA (test) daily disposable silicone hydrogel lens compared to the Invigor IB (control) lens that is identical to the marketed lens Select 1 Day, and is labelled with an investigational label for the purpose of this study.

This is a study to validate the performance of Invigor 1 (test) lenses when worn on a daily disposable wear modality over 1 week (for each lens).

The primary variables of interest are:

- Comfort and preference (subjective ratings)
- Vision (logMAR, and subjective ratings)
- Anterior ocular health (corneal staining and conjunctival staining, etc.)
- Discontinuation rate

[REDACTED]

[REDACTED]

[REDACTED]

[REDACTED]

[REDACTED]

[REDACTED]

[REDACTED]

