7.4.7 MASKING AND CONTROL OF STUDY MATERIALS

The contact lenses coding will be masked to both the investigator and participant. If standard labelling does not sufficiently mask the study material then over labelling will be performed. However

the safety information on the outer package label of the contact lens will not be covered and shall be clearly visible.

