12 DATA QUALITY ASSURANCE

12.1 STUDY MONITORING

Site qualification of the investigative site has been completed to ensure that the site facility is adequate, personnel are qualified and resources are satisfactory to conduct clinical studies for the Sponsor. The protocol will be reviewed by the investigators prior to enrollment of the first participant. This will involve an overview of the protocol, which includes information on study objectives, inclusion and exclusion criteria, study visits and adverse event reporting. Data collection forms will also be reviewed and this will provide an opportunity to discuss any questions.

Central study monitoring will involve regular study updates from the clinical site to the sponsor. The updates will include the number of participants enrolled, the number eligible, the number completed and whether there have been any unscheduled visits, discontinuations, significant or serious adverse events or major protocol deviations. These updates will be provided weekly.

Prior to final data lock, a close-out visit/discussion may be warranted to check for accuracy and completeness of records. The sponsor or sponsor's representatives will be authorized to gain access to the source documentation for the purposes of monitoring and auditing the study.

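### Could the used foils and unworn lenses brought back at Visits 2 and 3 unmask the investigator who grades the eyes?

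*Combined protocol and SAP*

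**What the plan says.** **Returns.** Section 7.4.6 has participants discard worn lenses daily but "retain the foils of all used lens packs and return them at their next study visit". It adds: "All unworn lenses will be collected from each study participant". No recipient is named for either. For lenses worn to a scheduled visit, it says "they may be either returned to the Sponsor or disposed, as detailed in the implementation protocol".

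**Masking of the material.** Section 7.4.7 states: "The contact lenses coding will be masked to both the investigator and participant". It continues: "If standard labelling does not sufficiently mask the study material then over labelling will be performed". Section 7.2 masks both participant and investigator and places the randomization scheme with an unmasked member of site staff. Section 7.1 gives the schedule to the research assistants.

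**Dispensing.** Sections 7.5.1 and 7.5.2 have lenses dispensed by support staff in a way that keeps participant and investigator masked. Section 7.5 also allows the investigator to provide them, on the same condition for the investigator.

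**Names and key.** The label text in section 7.4.1 gives one name to each lens type and says which is the test. Section 2 describes the test lens "compared to the Invigor IB (control) lens that is identical to the marketed lens Select 1 Day". Section 12.1 adds: "The protocol will be reviewed by the investigators prior to enrollment of the first participant".

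**Accounting.** Section 7.4.5 gives the running inventory and the replacement log to the site. Section 7.4.8 gives the final accounting to the investigator at study completion.

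**The concern.** The plan protects the mask when packs go out but has no matching sentence for when they come back. They come back at Visits 2 and 3, where the investigator grades surface and fit and performs slit-lamp biomicroscopy. Table 1 gives the two lenses the same material, water content, Dk/t, base curve, diameter and power range, so the name on the pack is an obvious place for the assignment to leak. Investigators also read a protocol that prints which name is the test.

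If a pack did show its name, the consequence would be real. With two lenses and two periods, one readable pack identifies the lens in both. The crossover would not remove the resulting bias, because an assessor's expectation attaches to the lens and not to the period.

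A smaller point is that section 7.2 keeps investigators masked until database lock, while section 7.4.8 does not say that the investigator's product accounting comes after lock.

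**Working it through.** The plan gives no figure to reproduce. The check has four steps.

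**1. How many occasions.** Returns fall at Visits 2 and 3, so 2 per participant (for unworn lenses this is inferred, since section 7.4.6 names no visit). From section 7.3, 30 target completers give 30 × 2 = 60 and 40 dispensed give 40 × 2 = 80, the maximum if everyone attends both visits.

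**2. Would the crossover cancel an assessor bias?** Let τ be the true test-minus-control difference, β the extra difference from an assessor's expectation, and π the period 2 minus period 1 effect. The period 1 minus period 2 difference is:

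- test first: (τ + β) − π
- control first: −(τ + β) − π

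Half the difference between the sequences is τ + β. The period effect drops out and β stays. The concern is right on this, but β is zero unless the assessor can tell the lenses apart. Everything turns on step 3.

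**3. Can a returned pack tell the assessor which lens it is, if the plan is followed?**

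- Section 7.4.7 sets its requirement by result: the coding is to be masked from the investigator. Over-labelling is triggered when the standard label does not achieve that.
- A lens name whose meaning is printed in a protocol the investigators review does not mask it from them. If the standard label shows that name where an investigator would see it, the section 7.4.7 condition is met and over-labelling is required.
- An over-label stays on the pack. It protects the return as it protected the dispensing.
- Section 7.5 lets the investigator hand lenses out, and under sections 7.5.1 and 7.5.2 lenses are inserted from the blister during Visits 1 and 2. The packs therefore already have to be safe near the investigator on the way out. Nothing in the documents makes the same packs less safe on the way back.

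A pack that unmasked the assessor would thus be a breach of section 7.4.7, not a result of following section 7.4.6.

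**4. Is the hand-over really unassigned?** The public text cannot settle this.

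- Section 7.5.2 has several redacted blocks, one directly after the surface and fit grading. Section 7.5.3 relies on 7.5.2 for its assessment steps.
- Table 3 has a row with a redacted name, marked for Visits 2 and 3 only.
- Section 7.4.6 already sends detail on lenses worn to visits to the implementation protocol, which is not among the documents and may also cover foils.

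None of these shows that a recipient is named, but together they mean its absence cannot be asserted.

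**The section 7.4.8 point.** Under section 12.2 data are recorded on forms in ink, so by study completion the gradings exist. Accounting done before lock could touch only the check of records that section 12.1 foresees, not the grading. No masking fault is shown for the replacement log in section 7.4.5.

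**The case for a change.** The strongest case for a change is that the authors recognised pack handling as a masking risk and wrote a safeguard for one direction only. The over-labelling rule is conditional in section 7.4.7 and only permissive in section 7.2, which also promises masked coding only as far as possible. Neither section mentions individual blister foils. The unmasked staff member in section 7.2 is tied to the randomization scheme, not to returns. One sentence naming that person would cost little and make the masking commitment checkable in both directions.

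Much of this stands as description. The visible text names no recipient, and the asymmetry with dispensing is real. What does not follow is a fault in the plan. The condition in section 7.4.7 is whether the material is sufficiently masked, so over-labelling is mandatory in exactly the case that worries us. That section speaks of the study material generally and does not exempt foils. Who takes a bag of foils at the desk is operating detail that a site normally settles in its procedures, and staff other than the investigator already handle dispensing.

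The reach is also limited. Comfort, preference and subjective vision are rated by the participant, who handles the packs in any case. Of the primary variables visible in section 2, the exposed part is mainly the investigator's grading of staining. Surface and fit are not listed there.

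**Conclusion.** No change to the plan is needed. Section 7.4.6 leaves a small operational gap in its visible text, and the masking rule in section 7.4.7 already covers the consequence. The occasions number 60 to 80, but no unmasking or bias is shown and none can be estimated from the documents. Sample size, power, alpha and the analysis are unaffected.

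This rests on two assumptions: that section 7.4.7 is carried out as written, including on foils if they carry the lens name, and that the site handles returns with ordinary care for the mask. A site wanting it in writing could say in the implementation protocol that returned foils and unworn lenses go to staff who do not grade. That is optional housekeeping. Moving the replacement log or the final product accounting to other staff would go further than any fault shown.

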7.4.7 MASKING AND CONTROL OF STUDY MATERIALS

The contact lenses coding will be masked to both the investigator and participant. If standard labelling does not sufficiently mask the study material then over labelling will be performed. However

the safety information on the outer package label of the contact lens will not be covered and shall be clearly visible.

7.4.8 ORDERING AND ACCOUNTABILITY OF STUDY MATERIALS

Both the Invigor IA (test) and the Invigor IB study lenses will be provided by the Sponsor.

The investigator must complete an accurate accounting of the study product at the completion of the study. A detailed inventory must be completed for study supplies. All unused and used materials will be returned to the Sponsor at the end of the study unless the investigator is otherwise directed by the study Sponsor.

7.5 VISIT SCHEDULE AND PROCEDURES

Prior to lens insertion, biomicroscopy (including corneal and conjunctival staining) will be completed at the screening assessment. When possible, the screening will be combined with the baseline assessment.

The contact lenses will be provided to participants by a research assistant / study coordinator / technician or the investigator (lenses will be provided to the investigator without unmasking the investigator).

The investigator should confirm with the participant that they are able to attend the follow-up visits within the visit window before enrolling them in the study.

It is anticipated that this study will involve 3 scheduled visits:

- Visit 1: Enrollment/ Screening/ Baseline/ Fitting/ Dispensing of lens pair #1 (either test or control lens);
- Visit 2: 1-week follow-up assessment of lens pair #1, & dispense of lens pair #2 (either test or control lens), 6-10 days after dispense of lens pair #1;
- Visit 3: 1-week follow-up assessment of lens pair #2, 6-10 days after lens pair #2 dispense and exit.

Visits that fall outside of the specified visit windows may be considered as unscheduled visits.

The Invigor IA (test) lenses will be worn for one week (6-10 days) and the Invigor IB (control) lenses will be worn for one week (6-10 days). Lens assessment visits will occur with each pair of lenses with options as described in Table 2.

At the completion of the one week period of wear with the first pair of lenses there will be a break of 10 minutes, followed by a dispense and assessment of the second pair of lenses. At the completion of the last visit, participants will exit the study.

Table 2 lists a summary of the study visits.

Table 2: Summary of study visits

Visit #	Visits	Visit length
1 – 0*	Screening and fitting	0.5 hrs
1 – 1**	Lens pair #1: dispense and baseline assessment	1.0 hrs.
2#	Progress assessment of lens pair #1, and dispense of lens pair #2 (6 to 10 days after lens pair #1 dispense)	1.5 hrs.
3	Progress assessment of lens pair #2, and Exit from Study (6 to 10 days after lens pair #2 dispense)	1.0 hrs.

* The 1-0 and 1-1 visits may be combined (to total 1.5 hrs)

#Lens pair #1 and Lens pair #2 may be either the Invigor IA (test) or Invigor IB (control)

7.5.1 VISIT 1: SCREENING / BASELINE VISIT / DISPENSING PAIR #1

Participant will be assigned a unique participant/Study ID number after signing the ICL. The investigator will determine participant eligibility using the inclusion and exclusion criteria. Ineligible participants will be discontinued from the study.

The following evaluations will be performed to assess eligibility according to the Inclusion and Exclusion Criteria at the screening and baseline visit:

- The patient is expected to attend the screening / baseline visit not wearing their habitual contact lens products.
- The participant will be required to read and sign an Informed Consent Form prior to enrolment. When the participant has signed the consent form, the participant will be considered to be enrolled in to the study.
- Participant demographics and medical history (age, sex, race and ethnicity, medical conditions, medications, allergies)
- Contact lens history (own lens information, and wear time)
- Baseline visual acuity with spectacles or spectacle refraction.
- Auto refraction/auto keratometry: Horizontal and Vertical K readings (D)
- Sphero-cylindrical refraction (D), and best sphere refraction (D) & monocular & binocular distance visual acuity (high contrast) (logMAR)
- Slit lamp biomicroscopy will be assessed according to the approved study biomicroscopy CRF (Appendix 4).

- The investigator will confirm that the patient meets the criteria set out in the inclusion criteria, and none of the exclusion criteria and is eligible to continue in the study.
- The participant will be assigned a randomization ID and the first pair of contact lenses (either test or control) will be selected according to the randomization table.
- Contact lens power and fit may be evaluated at the screening visit or at the baseline visit.

[REDACTED]

[REDACTED]

[REDACTED]

[REDACTED]

- The contact lenses will be dispensed by a research assistant / study coordinator / technician (in a manner which does not unmask the participant and investigator).
- The lenses will be inserted by the participant from the blister pack as described in Section 7.4.3 of the Protocol.
- The contact lenses will be fitted and allowed to settle (Appendix 3).
- Initial subjective ratings (Appendix 16) include:

- Initial comfort (0-100 scale) and comments

[REDACTED]

[REDACTED]

- Vision quality / clarity (0-100 scale) and comments

[REDACTED]

- The lens fit will be assessed for fit acceptance (acceptable or not acceptable) and absence of lens defects. If the fit is acceptable and there are no defects, the participant will be allowed to sit for 10 minutes to allow for the lenses to settle.
- Monocular over refraction will be done to determine if a different power is needed.

[REDACTED]

[REDACTED]

[REDACTED]

- Change lens prescription to that noted by over-refraction, if needed. Repeat subjective ratings after lens settling.

- Monocular and binocular logMAR visual acuity (4M) will be recorded with high contrast letters under high and low room illumination*.

[REDACTED]

[REDACTED]

- Lens fitting assessment, according to the guidelines in Appendix 3.
- Monocular lens surface and fit will then be assessed and graded according to the CVI grading scales (Appendix 5).

[REDACTED]

- The participant will be instructed to wear the study lenses for at least 8 hours, and 5 days per week.
- Participants will be provided contact lenses for wear till the next scheduled visit.

- At end of visit the participant will be reminded to return for the next scheduled visit of the first pair.

7.5.2 VISIT 2: ASSESSMENT OF PAIR #1 AND DISPENSING PAIR #2

This visit will occur 6-10 days after dispense of lens pair #1.

Participants will be asked to wear lenses for **at least two hours** prior to the visit appointment.

Participants who attend without wearing lenses for the specified period will be rescheduled.

- The participant will be asked to score their subjective response as detailed in CVI Grading scales (Appendix 18D).
- The following will be recorded at the one week visit.
 - Hours of lens wear prior to the appointment

[REDACTED]
[REDACTED]

- Binocular comfort at insertion, during the day, end of the day, during the last week
- Overall comfort (0-100 scale), during the last week

[REDACTED]
[REDACTED]

- Binocular vision quality / clarity of vision during the last week (0-100 scale)
- Binocular vision quality / clarity of vision at night during the last week if applicable (0-100 scale)

[REDACTED]
[REDACTED]
[REDACTED]

- Comments by participants

- Unscheduled lens replacements (Y/N) OD and / or OS
- Monocular and binocular logMAR visual acuity (4M) will be recorded with high contrast letters under high and low room illumination.
- Monocular lens surface and fit will then be assessed and graded according to the CVI grading scales. [REDACTED]

- The lenses will be removed and retained in the CCLR (see Section 7.4.6 for disposing consumables).
- Slit lamp biomicroscopy will be assessed according to the approved study biomicroscopy CRF (Appendix 4).
- There will be a break before insertion of pair 2 (of 10 minutes).
- The same procedures will be followed for pair 2 as mentioned in section 7.5.1.
- The contact lenses will be dispensed by a research assistant / study coordinator / technician (in a manner which does not unmask the participant and investigator).
- The lenses will be inserted by the participant from the blister pack as described in Section 7.4.3.

Procedures of lens assessment and dispense will be repeated as detailed in section 7.5.1 for Baseline visit / Dispensing Pair #1.

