7.3.1 INCLUSION CRITERIA

A person is eligible for inclusion in the study if he/she:

- Is at least 17 years of age and has full legal capacity to volunteer;
- Has had a self-reported oculo-visual examination in the last two years;
- Has read, understood, and signed the information consent letter;
- Is willing and able to follow instructions and maintain the appointment schedule;
- Has a visual acuity of 20/30 or better (in each eye) with their habitual vision correction, or 20/20 best-corrected vision (for binocular distance acuity);
- Must be able to achieve 20/30 or better (in each eye) with the study lenses;
- Currently wears soft contact lenses for at least 3 days per week, 8 hours each day;
- Requires spectacle lens powers between -0.75 and -06.50 diopters sphere (0.25D steps);
- Has no more than 0.75 diopters of refractive astigmatism;
- Has clear corneas and no active* ocular disease;
- Has not worn lenses for at least 12 hours before the examination.

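### The in-clinic initial comfort and vision ratings start from a different eye state in each period, so any lens comparison of them should carry a period term (minor)

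*Combined protocol and SAP*

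**What the plan says.** Protocol section 7.5.1 has each participant rate the lenses at first insertion in the clinic: "Initial comfort (0-100 scale) and comments", and vision quality on the same scale. Section 7.5.2 repeats this for the second pair: "The same procedures will be followed for pair 2 as mentioned in section 7.5.1".

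The eye's state before the two insertions differs.

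- **Pair #1 (Visit 1).** Section 7.3.1 requires that the participant "Has not worn lenses for at least 12 hours before the examination". Section 7.5.1 adds: "The patient is expected to attend the screening / baseline visit not wearing their habitual contact lens products". The footnote to Table 2 says "The 1-0 and 1-1 visits may be combined (to total 1.5 hrs", so screening and dispensing may also be separate. No number of lens-free hours is given for a separate dispensing visit.
- **Pair #2 (Visit 2).** Participants are asked to "wear lenses for at least two hours prior to the visit appointment" and are rescheduled if they have not. Pair #1 is then removed, the slit-lamp examination follows, and then: "There will be a break before insertion of pair 2 (of 10 minutes".

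Section 2 lists subjective comfort and vision ratings among the primary variables. Section 3 randomises which lens is worn first. The one-week visits separately collect "Binocular comfort at insertion, during the day, end of the day, during the last week".

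**The concern.** Each participant's two in-clinic insertion ratings come from different starting states, and the difference always runs the same way: pair #1 on a rested eye, pair #2 on an eye that has just worn the other lens. If starting state shifts the rating, the test-minus-control difference contains the lens effect plus that shift in one sequence, and minus it in the other. An analysis that pairs the ratings without regard to period puts the shift into the error term. If the sequences are unequal in size, part of it also enters the estimated lens difference. The hypothesis in section 2.1 is that the test lens does as well as or better than control, so both avoidable noise and avoidable bias bear on how the result is read.

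**Working it through.** **The plan's own figure.** Section 11.1 gives about 40 dispensed for about 30 completing. That is a loss of 10/40 = 25%, and 30/(1 − 0.25) = 40. The rest of the sample-size text is redacted, so no SD, effect size or power can be reproduced.

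**Inputs.** From the plan: n = 30 completing, alpha 0.05 without multiplicity adjustment, a 0-100 scale, randomised order. Assumed, because the documents do not give them: period effect π (period 2 minus period 1) of 5 or 10 points; SD of within-person differences σ of 10 or 15 points, net of period; a two-sided test. The allocation ratio and blocking are not in the visible text, so several splits are shown.

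**Model.** Let τ be the test-minus-control effect. The expected paired difference is τ + π in the control-then-test sequence (CT) and τ − π in the test-then-control sequence (TC). Hence

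- raw mean difference = τ + π(n_CT − n_TC)/n;
- SD seen by the raw analysis = √(σ² + π²[1 − ((n_CT − n_TC)/n)²]);
- period-adjusted estimate = (mean difference in CT + mean difference in TC)/2, in which π cancels, with SE = (σ/2)√(1/n_CT + 1/n_TC).

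**Bias of the raw comparison.** For π = 5:

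- 15/15: 0
- 16/14: 5 × 2/30 = 0.3
- 18/12: 5 × 6/30 = 1.0
- 20/10: 5 × 10/30 = 1.7

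These double for π = 10.

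**Precision at 15/15.** With π = 5, √(100 + 25) = 11.2 in place of 10, and √(225 + 25) = 15.8 in place of 15. The intervals are about 12% and 5% wider. With π = 10 the SDs become 14.1 and 18.0.

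**Type I error of the raw paired t-test** (simulation, nominal 0.05):

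| σ | π | 15/15 | 18/12 | 20/10 |
|---|---|---|---|---|
| 10 | 5 | 0.03 | 0.05 | 0.10 |
| 10 | 10 | 0.01 | 0.05 | 0.17 |
| 15 | 5 | 0.04 | 0.05 | 0.07 to 0.08 |
| 15 | 10 | 0.02 | 0.05 | 0.13 |

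At 18/12 the bias and the inflated error term roughly cancel in the test, but the estimate is still biased. With a period term the simulated error was 0.047 to 0.051 in every cell.

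**Power for an assumed 6-point difference at 15/15, raw versus adjusted.** For σ = 10: 0.83 versus 0.88 (π = 5) and 0.65 versus 0.89 (π = 10). For σ = 15: 0.52 versus 0.57 and 0.40 versus 0.56.

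**How likely is imbalance?** Under simple randomisation, a difference of 6 or more among 30 has probability 0.36. If 20/20 were dispensed and 10 lost at random, it is 0.065, and a 20/10 split is 0.0004.

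**The case against.** The strongest reply is that randomised order already deals with this. Each lens is rated in both states, so starting state follows period and not lens, and with balanced sequences the mean comparison is unbiased. That stands. A reader might infer from the schedule that lens and starting state are confounded; the documents do not support that.

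A reader might also infer that the plan compares these ratings by raw pairing. It cannot be shown. Section 11.3 names the paired t-test and Wilcoxon test only for right eye versus left eye, and part of that section is redacted, so a period term may already be there. Nor does the visible text make the in-clinic rating the basis of the comfort conclusion. The one-week ratings are not affected in this way.

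Three further limits stand. Slit-lamp examination precedes both insertions, so it is not part of the asymmetry. The 12-hour figure is tied to the examination and may not cover a separate dispensing visit. A large imbalance is plausible under simple randomisation but unlikely under a balanced schedule with random loss.

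Unequal carry-over would bias even a balanced comparison, and a period term would not cure it. The documents give no data suggesting it, and Table 1 lists the same material, water content, Dk/t, base curve and diameter for both lenses.

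What survives is narrow: the difference in starting state is in the text, applies by design, and can be handled in the analysis with data already collected.

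**Conclusion.** The point holds as a minor one. The schedule builds a period effect into the in-clinic initial comfort and vision ratings. An analysis that ignored it would be unbiased but less precise and conservative at equal sequence sizes, and biased by π × (difference in sequence sizes)/n otherwise. Type I error would range from about 0.03 at 15/15 to about 0.10 at 20/10 for an assumed 5-point effect and SD of 10. All these sizes rest on assumed period effects, SDs and splits; only the direction and the formula follow from the design.

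It would be going too far to replace the in-clinic rating with the recalled one-week rating of insertion comfort. An immediate and a recalled rating measure different things, and the recalled one can have a period effect of its own.

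**What to change.** Add to section 11.3 that any lens comparison of the in-clinic initial comfort and vision ratings includes a period term. Equivalently, compare within-person period differences between the two randomised sequences; if a rank method is planned, use a rank-sum test on those differences. Show these ratings by visit, and report by sequence how many participants have both ratings and how many complete. If the redacted text already specifies this, a sentence confirming it is enough. Keep the one-week insertion-comfort rating as a separate result, and leave the break and the visit schedule unchanged.

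The cost is a sentence or two and one degree of freedom, with no new data. At 15/15 the adjusted SE is the same as with no period effect: for σ = 10, (10/2)√(1/15 + 1/15) = 1.83. At 20/10 it is (10/2)√(1/20 + 1/10) = 1.94, about 6% larger, which is the price of removing the bias. Showing the ratings by visit also gives a randomised comparison at Visit 1 that no study-lens carry-over can touch, though between participants and so less precise.
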